**Table LB 3 Safety laboratory measurements - coagulation (Full analysis set)**

Use the same format as for Table LB 1.

**Table LB 4 Safety laboratory interpretations - urinalysis (Full analysis set)**

Use the same format as for Table LB 1.

### 10.2.3 Secondary endpoint(s)

#### 10.2.3.1 Unified Dyskinesia Rating Scale (UDysRS) total score

**Table UD 1 UDysRS total score for all Parts (Full analysis set)**

Result category	Assessment timepoint		NLX-112 (N=XX)	Placebo (N=XX)	Total (N=XX)
Measured value	[Assessment timepoint 1]	n	xx	xx	xx
		Mean (SD)	x.xx (x.xx)	x.xx (x.xx)	x.xx (x.xx)
		Median (Min, Max)	x.xx (x.x, x.x)	x.xx (x.x, x.x)	x.xx (x.x, x.x)
	[Assessment timepoint 2]	n	xx	xx	xx
		...	...	...	...
Absolute change from baseline	[Assessment timepoint 2]	n	xx	xx	xx
		Mean (SD)	x.xx (x.xx)	x.xx (x.xx)	x.xx (x.xx)
		Median (Min, Max)	x.xx (x.x, x.x)	x.xx (x.x, x.x)	x.xx (x.x, x.x)
	[Assessment timepoint 3]	LMM a p-value	xxxxx b	xxxxx c	xxxxx d
		n	xxxxx	xxxxx	xxxxx
		...	...	...	...
Relative change from baseline (%)	[Assessment timepoint 2]	n	xx	xx	xx
		Mean (SD)	x.xx (x.xx)	x.xx (x.xx)	x.xx (x.xx)
		Median (Min, Max)	x.xx (x.x, x.x)	x.xx (x.x, x.x)	x.xx (x.x, x.x)
	[Assessment timepoint 3]	n	xxxxx	xxxxx	xxxxx
		...	...	...	...

a) Linear mixed model (LMM) with treatment, visit and the interaction treatment\*visit as fixed categorical effects and subject within treatment as a random effect. The baseline value of the dependent variable has been included in the model as a continuous covariate. Kenward-Roger's approximation for degrees of freedom will be used.

b) p-value for the difference between NLX-112 at the assessment timepoint and at baseline.

c) p-value for the difference between placebo at the assessment timepoint and at baseline.

d) p-value for the difference between NLX-112 and placebo absolute change from baseline at the assessment timepoint.

Data based on the Full analysis set. The session marked as most severe for Part III and IV have been used. For Part III, the highest score for each individual questionnaire item has been used. All UDysRS item scores for Part I, II, III and IV have been summarized pre patient and assessment timepoint and used as input data to the table. N: Number of observations. SD: Standard deviation. NC: Not calculated - number of evaluable observations less than 3. NA: Not available - no evaluable observations. SAS program: [PROGRAM NAME].sas. Run by: [USERNAME] YYYY-MM-DDTHH:MM:SS. Data extracted at: YYYY-MM-DDTHH:MM:SS

Produce the table above for PPS as well, providing there is any de facto difference between the analysis sets. If the LMM is performed using transformed data, insert a footnote about this as well. If the LMM approach is dropped in favour of non-parametric tests, update the table and footnotes accordingly.

**Table UD 2 UdysRS total score for Part III and IV – Most severe assessment session and highest questionnaire item score (Full analysis set)**

Use the same format as for Table UD 1. Produce the table above for PPS as well, providing there is any de facto difference between the analysis sets. If the LMM is performed using transformed data, insert a footnote about this as well. If the LMM approach is dropped in favour of non-parametric tests, update the table and footnotes accordingly.

**Table UD 3 UdysRS total score for Part III and IV – Average of assessment sessions and highest questionnaire item score (Full analysis set)**

Use the same format as for Table UD 1, but update the explanatory footnote to reflect the content of the table. Produce the table above for PPS as well, providing there is any de facto difference between the analysis sets. If the LMM is performed using transformed data, insert a footnote about this as well. If the LMM approach is dropped in favour of non-parametric tests, update the table and footnotes accordingly.

**Table UD 4 UdysRS total score for Part III– Most severe assessment session and sum of questionnaire item scores (Full analysis set)**

Use the same format as for Table UD 1, but update the explanatory footnote to reflect the content of the table. Produce the table above for PPS as well, providing there is any de facto difference between the analysis sets. If the LMM is performed using transformed data, insert a footnote about this as well. If the LMM approach is dropped in favour of non-parametric tests, update the table and footnotes accordingly.

**Table UD 5 UdysRS total score for Part III– Average of assessment sessions and sum of questionnaire item scores (Full analysis set)**

Use the same format as for Table UD 1, but update the explanatory footnote to reflect the content of the table. Produce the table above for PPS as well, providing there is any de facto difference between the analysis sets. If the LMM is performed using transformed data, insert a footnote about this as well. If the LMM approach is dropped in favour of non-parametric tests, update the table and footnotes accordingly.

*10.2.3.2 ON Time Without Troublesome Dyskinesia*

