#### **7.2 Secondary objective**

To assess the preliminary efficacy of NLX-112 treatment in reducing troublesome LID.

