### 9.3 Number of patients

A total of 24 patients will be randomized in the study.

To account for potential drop-outs, additional patients may be included in the study. For replacements of patients who discontinue from the study, see Section 9.8.

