#### 4.3 Randomization and number of subjects

On Day 1, patients were randomized to receive either NLX-112 or placebo with the ratio 2:1 for active treatment to placebo. This will give approximately 16 patients who received NLX-112 and 8 patients who received placebo in the study. In addition, approximately the same ratio was intended to be attained within each site. The study used competitive enrolment between 5 sites.

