## 5 STATISTICAL AND ANALYTICAL PLANS

### 5.1 Statistical hypotheses

Hypotheses tests will be performed at the 5% alpha level with the aim of proving superiority of NLX-112 compared to placebo on the change from baseline on a number of efficacy parameters. Any inference of superiority of NLX-112 compared to placebo will be based on these tests. Further testing within each treatment (NLX-112 or placebo respectively) at the 5% alpha level will be done with the aim of proving a beneficial shift from baseline, as a result of the IMP intervention.

Considering the small dimension of the study and the many tests performed, statistically significant findings should be viewed more as indicative results rather than confirmatory.

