### 5.2 Sample size calculation

No formal sample size calculation has been performed. The sample size of 24 patients is considered sufficient to evaluate the primary objective and to allow for a preliminary efficacy evaluation.

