## 5.7 Significance level

All hypothesis testing will be two-sided, using a 5% significance level ( $\alpha=0.05$ ).

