### 9.2 Analysis of secondary endpoints

#### 9.2.1 *Statistical inferential analysis of efficacy endpoints*

Absolute change from baseline in efficacy endpoints (secondary and exploratory endpoints) will generally be analysed using a linear mixed model with treatment, visit and the interaction

treatment\*visit as fixed categorical effects and subject within treatment as a random effect. The baseline value of the dependent variable will be included in the model as a continuous covariate, to account for possible differences in change from baseline outcomes due the starting baseline level. Visit will be modelled as a repeated effect. Kenward-Roger's approximation for degrees of freedom will be used.

Providing a significant type III F-test for the interaction effect treatment\*visit, differences between least square estimates of NLX-112 and placebo for the same visit (i.e. from the interaction term treatment\*visit, where visit is the same for both NLX-112 and placebo) will be estimated and the corresponding p-value will be presented in tables. In addition, differences between least square estimates of each post-baseline visit and baseline for NLX -112 and placebo respectively (i.e. from the interaction term treatment\*visit, where treatment is the same for the post-baseline and the baseline visit) will be estimated and the corresponding p-value will be presented in tables.

The model proposed above will be used for FAS and is valid, as long as the underlying data is missing at random (MAR). As a sensitivity analysis, the model will also be run for PPS, serving as a validity check for the main FAS analysis. The sensitivity analysis will be a complete case analysis, i.e., only patients with no missing data for the dependent variable will be used.

Model diagnostics, for example Shapiro-Wilk's test for a normally distributed residual term and Leven's test for the homoscedasticity assumption of the residual term as well as Q-Q plots and plotting residuals vs. predicted values, will be performed. If model assumptions are deemed to be violated, an attempt will be made to transform the dependent variable in order to fulfil model diagnostics.

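### The efficacy tables plan a mixed-model p-value but no adjusted difference or confidence interval, and SAP 9.2.1 makes even the by-visit contrast depend on a significant interaction test

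*SAP*

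**What the plan says.** The secondary objective (Protocol 7.2) is "To assess the preliminary efficacy of NLX-112 treatment in reducing troublesome LID". Protocol 8.3 adds that the results are meant to inform the design of later studies. SAP 5.1 frames the efficacy tests "with the aim of proving superiority of NLX-112 compared to placebo on the change from baseline on a number of efficacy parameters", while cautioning that significant findings are indicative rather than confirmatory.

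SAP 9.2.1 specifies a linear mixed model for absolute change from baseline, with treatment, visit, their interaction and the baseline value as a covariate. Provided that the type III F-test for the interaction is significant, differences between the LS estimates of the two arms at the same visit "will be estimated and the corresponding p-value will be presented in tables". No other between-arm estimate is named for the case where that test is not significant.

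The table shells follow suit. Table UD 1 (SAP 10.2.3.1) gives n, mean (SD) and median (min, max) by arm and visit for the measured value, absolute change and relative change. Its only model row is an LMM p-value. The between-arm entry, placed in the Total column, is defined in a footnote as the "p-value for the difference between NLX-112 and placebo absolute change from baseline at the assessment timepoint". UD 2 to UD 5, ON 1, UP 1, UP 2, DA 1, IC 1 and ES 1 reuse this format. CG 1 and KP 1 have their own shells, again with a p-value as the only model output, and PD 1 and HA 1 reuse KP 1.

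CI and LS are in the SAP's abbreviation list, but no analysis section or table plans a confidence interval. The introduction to SAP Section 9 describes Section 10 as the full definition of the output.

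**The concern.** An early study of this size is most useful for an effect estimate and its uncertainty. There was no power or precision target: "No formal sample size calculation has been performed" (SAP 5.2). With about 8 placebo patients, a non-significant p-value cannot distinguish a negligible effect from a large one measured poorly. The planner of the next trial would need the baseline-adjusted difference and its interval, which the planned tables do not contain. The raw means that are shown are not the quantities that the model tests.

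The interaction condition adds a second problem. Interaction asks whether the treatment difference changes between visits, not whether there is a difference. A steady benefit at Day 28 and Day 42 is a favourable result, yet it is the pattern least likely to satisfy the condition.

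**Working it through.** **Inputs from the documents**
- Total: "A total of 24 patients will be randomized in the study" (Protocol 9.3).
- Split: "This will give approximately 16 patients who received NLX-112 and 8 patients who received placebo in the study" (SAP 4.3). At 2:1, 24 × 2/3 = 16 and 24 × 1/3 = 8, which agrees.
- Level: "All hypothesis testing will be two-sided, using a 5% significance level" (SAP 5.7).
- SD of change, expected effect and dropout are not given. Results are therefore in SD units, and anything further is an assumption.

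The plan states no power or precision figure to reproduce.

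**Half-width of the 95% CI, unadjusted, one visit, 16:8**
- SE = SD × √(1/16 + 1/8) = 0.433 SD.
- t(0.975, 22 df) = 2.074.
- Half-width = 2.074 × 0.433 = 0.898 SD, so the full width is about 1.80 SD.
- For an assumed SD of change of 5, 8, 10, 12 or 15 UDysRS points, this is ±4.5, 7.2, 9.0, 10.8 or 13.5 points.

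**Sensitivity to the assumptions**
- Assumed 14:7 evaluable: SE = √(1/14 + 1/7) = 0.463 SD and half-width 0.969 SD.
- Baseline covariate, 16:8, one df fewer: the half-width is 0.900 × √(1 − ρ²) SD, where ρ is the assumed correlation of baseline with change. This gives 0.86 SD at ρ = 0.3, 0.78 at 0.5 and 0.64 at 0.7.

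**What a p-value alone leaves unsaid (16:8, unadjusted)**

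| Observed difference (SD) | Two-sided p | 95% CI (SD) |
|---|---|---|
| 0.57 | 0.20 | −0.33 to 1.47 |
| 0.60 | 0.18 | −0.30 to 1.50 |
| 0.90 | 0.05 | 0.00 to 1.80 |
| 1.22 | 0.01 | 0.32 to 2.12 |

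Power of the same t-test is about 20% for a true difference of 0.5 SD, 42% for 0.8 SD and 60% for 1.0 SD. A non-significant result is therefore quite likely even when the effect is large.

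**The interaction condition**
Suppose that the visit factor has only the levels Day 28 and Day 42 and that the true treatment difference is the same at both. The interaction is then zero. Its test at the 5% level is significant about 5% of the time, so followed as written the by-visit contrast would be omitted about 95% of the time. SAP 9.2.1 also mentions contrasts with baseline, so it is unclear whether baseline is meant to be a level of visit. The 5% figure depends on its not being one. The Table UD 1 footnotes do not mention the condition at all, so the shell and 9.2.1 do not quite agree.

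**The case against.** A reader might infer that the trial would report no effect size, only p-values. The documents do not support that. UD 1 and KP 1 show n, mean (SD) and median of change by arm and visit, and CG 1 shows the same summaries of the CGI-C rating, which is itself a measure of change. A crude difference and CI can be derived from these. What cannot be recovered is the baseline-adjusted estimate, drawn from both visits with Kenward-Roger degrees of freedom, to which the p-value belongs.

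Nor is it right that the SAP fails to estimate the difference. It does so when the interaction condition is met; the gap is in what is tabulated. The documents also do not forbid an interval in the study report: Protocol 15.8.1 calls for an ICH E3 report of the analyses and results. But nothing commits to one, and choosing to add it after unblinding would be a post hoc decision.

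The half-widths describe a trial of 24 patients, not the omission. A CI row would not narrow them. The 0.90 SD figure is also not from the SAP's own model, so it should be read with the range above.

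Finally, efficacy is secondary to safety, and Protocol 17.1 and SAP 5.8 call the tests descriptive or exploratory. The omission biases nothing and loses no data. That limits its seriousness, but it also strengthens the case for showing estimates: if the tests are only indicative, the estimate and its interval are the main efficacy result.

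**Conclusion.** The point holds in this form: the adjusted by-visit difference is estimated only after a significant interaction test, and only its p-value is planned for display. Followed as written, the SAP tabulates no baseline-adjusted effect and no CI for any efficacy endpoint. With a similar effect at Days 28 and 42, it would usually report no between-arm contrast. The latter assumes that visit has post-baseline levels only.

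The interval left untabulated is wide. Its half-width runs from about 0.64 SD (assumed correlation 0.7) to 0.97 SD (assumed 14:7, no covariate), and is 0.90 SD for 16:8 without adjustment. The change is worth making before unblinding, but it does not call the design or the data into question.

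**What to change.** 1. In SAP 9.2.1, delete the requirement for a significant treatment-by-visit F-test before the by-visit contrasts are estimated.
2. Add the LS mean (SE) per arm and the LS mean difference, NLX-112 minus placebo, with two-sided 95% CI at Days 28 and 42, whatever the interaction result. This applies to UD 1 and the tables that reuse it (UD 2 to UD 5, ON 1, UP 1, UP 2, DA 1, IC 1, ES 1), to CG 1, and to KP 1 with PD 1 and HA 1.
3. If a Box-Cox transformation is used, state the scale on which the difference and CI are reported.
4. For the rank-sum fallback, add the Hodges-Lehmann shift with 95% CI and state that it is on the relative-change scale. It is then not directly comparable with the absolute-change LS difference.

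The cost is a small amount of programming and a change to one pre-specified condition. No new data or patients are needed. Items 1 and 4 go beyond table formatting, so they should be recorded as SAP changes before the code is broken.

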**Table ON 1 ON Time Without Troublesome Dyskinesia (Full analysis set)**

Use the same format as for Table UD 1. Add a footnote stating that the sum of records of ON Without Dyskinesia plus ON With Non-troublesome Dyskinesia for the 2\*24 hours measurements prior to each visit has been used as input data for each patient respectively. Produce the table above for PPS as well, providing there is any de facto difference between the analysis sets. If the LMM is performed using transformed data, insert a footnote about this as well. If the LMM approach is dropped in favour of non-parametric tests, update the table and footnotes accordingly.

*10.2.3.3 Unified Parkinson's Disease Rating Scale (UPDRS)*

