##### **7.2.1 *Secondary endpoints***

- Change from baseline at the final efficacy clinic visit (Day 42) in the Unified Dyskinesia Rating Scale (UDysRS) total score [Timeframe: Baseline to Day 42]. Patients will be challenged with 150% of their standard L-DOPA dose (maximum L-DOPA dose 250 mg) 30 minutes prior to the first UDysRS assessment.

- Change from baseline in UDysRS total score at Day 28, after a 150% L-DOPA dose challenge.
- Change from baseline in total objective score (Parts III, IV) of the UDysRS at Day 28 and Day 42, after a 150% L-DOPA dose challenge.
- Change from baseline in ON Time Without Troublesome Dyskinesia (ON Without Dyskinesia plus ON With Non-troublesome Dyskinesia) based on a PD Home Dyskinesia Diary.
- Change from baseline in Unified Parkinson's Disease Rating Scale (UPDRS) scores (Part III, motor examination).
- Change from baseline in UPDRS combined scores (Parts I, II, III and IV).
- Clinical Global Impression of Change (CGI-C) in overall PD symptoms
- Change from baseline in dyskinesia scores measured by the Kinesia 360 (Great Lakes Neurotechnologies, Inc) wearable dyskinesia assessment system.

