### 11.3.3 ***PD Home Dyskinesia Diary***

A PD Home Dyskinesia Diary (electronic) will be completed by the patients and/or caregiver with concordance in ON time with dyskinesia between study staff and patient. The diary is integrated in the Kinesia 360 wearable dyskinesia assessment system (Section 11.3.6) and is based on the PD Home Diary developed by Hauser et al 2004 [26]. The diary will be used to score 5 different conditions in 30-minute time intervals during 2x24 hours prior to Visit 2, Visit 6 and Visit 7:

- ASLEEP;
- OFF;
- ON (i.e., adequate control of PD symptoms) without dyskinesia;
- ON with non-troublesome dyskinesia;
- ON with troublesome dyskinesia.

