**Table 2 Changes in the planned statistical analyses**

Change category	Timing of change	Description of change	Reason for change	Responsible for change
Change in the SAP compared to the CSP	Prior to DBL	The safety analysis set has been omitted.	Safety evaluations based on FAS is considered sufficient.	[name]
Change in the SAP compared to the CSP	Prior to DBL	The Chi2 test for the ON Time Without Troublesome Dyskinesia analysis has been replaced with a linear mixed model approach.	The CSP prescribes that a chi-square test be performed for ON Time Without Troublesome Dyskinesia data for the whole study period. As there are multiple measurements per patient and visit, it is not clear how this can be implemented. Hence a shift to a mixed model approach has been adopted.	[name]
Change in the SAP compared to the CSP	Prior to DBL	Wilcoxon signed rank tests have been replaced with linear mixed modeling with a non-parametric back-up plan should model assumptions fail.	In order to use all available data in the same model, potentially resulting in higher power in the analyses, a mixed model approach has been adopted instead.	[name]
Change in the SAP compared to the CSP	Prior to DBL	The Kinesia 360 wearable dyskinesia assessment system and PD home dyskinesia diary data for up to 4*24 hours prior to Visit 6 and 7 is included in the analyses.	The CSP prescribes data from only up to 2*24 hours to be used in Kinesia 360 wearable device and home diary analyses. However, using the cut-off point of 4*24 hours prior to Visit 6 and 7 respectively was deemed medically acceptable, whereas at the same time minimizing the amount of missing data in the corresponding analyses.	[name]

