### **9.2.3      ON Time Without Troublesome Dyskinesia**

Change from baseline in ON Time Without Troublesome Dyskinesia (ON Without Dyskinesia plus ON With Non-troublesome Dyskinesia) based on a PD Home Dyskinesia Diary will be summarized using descriptive statistics for all assessment time points. In this analysis, the number of records of ON Without Dyskinesia plus ON With Non-troublesome Dyskinesia divided by the number of non-missing awake records (sleeping records are excluded) for all measurements prior to Visit 2 and for all measurements from 4\*24 hours prior to and up until Visit 6 and 7 respectively will be used as input data for each patient respectively. If there is not

at least 8 hours recorded data available for each patient and visit window, the corresponding timepoint is set to missing for the patient. ON Time Without Troublesome Dyskinesia will be analysed using inferential statistics as described under 9.2.1 above.

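### SAP Section 9.2.3 and the Table ON 1 footnote describe the ON-time input incompatibly (share of awake records against sum of records, over different windows), and the 8-hour minimum does not say whether sleep counts

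*SAP*

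**What the plan says.** Protocol Section 7.2.1 names the endpoint: "Change from baseline in ON Time Without Troublesome Dyskinesia (ON Without Dyskinesia plus ON With Non-troublesome Dyskinesia) based on a PD Home Dyskinesia Diary". It gives no unit. Protocol Section 11.3.3 says the diary scores "5 different conditions in 30-minute time intervals during 2x24 hours prior to Visit 2, Visit 6 and Visit 7". One of the five conditions is ASLEEP.

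SAP Section 9.2.3 takes the records of ON without dyskinesia plus ON with non-troublesome dyskinesia, "divided by the number of non-missing awake records (sleeping records are excluded"). The window is "for all measurements prior to Visit 2 and for all measurements from" 4*24 hours before Visits 6 and 7. Baseline therefore has no stated cap. A timepoint is set to missing unless there is "at least 8 hours recorded data available for each patient and visit window".

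SAP Table 2 records the wider post-baseline window as a deliberate change, covering "PD home dyskinesia diary data for up to" 4*24 hours, because "using the cut-off point of 4*24 hours prior to Visit 6 and 7 respectively was deemed medically acceptable" and it reduces missing data. It has no entry for expressing ON time as a share of awake records.

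The SAP display instruction for Table ON 1 (Section 10.2.3.2) says: "Add a footnote stating that the sum of records of ON Without Dyskinesia plus ON With Non-troublesome Dyskinesia" for the 2*24 hours before each visit was the input for each patient.

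**The concern.** Section 9.2.3 and the Table ON 1 instruction are both current SAP text, and the objectives table in SAP Section 4.2 sends the reader to both for this endpoint. The opening of SAP Section 9 says that Section 10 defines the output completely, so the shell cannot simply be treated as subordinate. Table ON 1 also borrows the Table UD 1 layout, which shows no unit. The footnote is then the table's only statement of what was measured and over which hours.

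Two outcomes are possible. A programmer who follows the footnote produces a count with no denominator, in a study whose SAP expects incomplete diaries and generally imputes nothing (SAP Section 5.9). A programmer who follows 9.2.3 produces a share under a footnote that calls it a sum over a different window.

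The minimum-data rule raises a smaller question. It counts recorded data, ASLEEP is a recorded state, and the denominator leaves ASLEEP out. The rule may therefore not protect the denominator it is there to protect.

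**Working it through.** The documents give no expected value, completion rate or power figure for this endpoint, so there is no plan figure to reproduce. The check is a comparison of texts plus record counts.

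**1. The two descriptions side by side**

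| | SAP 9.2.3 | SAP Table ON 1 footnote |
|---|---|---|
| Metric | share of non-missing awake records | sum of records |
| Baseline window | all measurements before Visit 2 | 2*24 h |
| Visits 6 and 7 window | 4*24 h (agrees with Table 2) | 2*24 h |

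They differ on all three rows. For comparison, the wearable endpoint is consistent: SAP Section 9.2.6 and the Table DA 1 footnote both use the mean.

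**2. What the sum does when diaries are incomplete**

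From the documents: 30-minute records, so 2 per hour, 48 per 24 h and 96 per 2*24 h. Assumed, because the documents do not give them: 16 awake hours a day, and a share p of awake time in ON without troublesome dyskinesia that is the same at every visit, so the true change is 0.

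Sum in hours = p × awake hours recorded. With p = 0.60:

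- complete two-day diary: 2 × 16 × 0.60 = 19.2 h
- one complete day: 16 × 0.60 = 9.6 h, an apparent change of −9.6 h
- 8 awake hours recorded: 8 × 0.60 = 4.8 h, an apparent change of −14.4 h

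The share is 60% in every case, so its change is 0. In general the artefact is p × the awake hours not recorded. For the 8-hour diary that is p × (32 − 8), which gives 9.6 h at p = 0.40 and 19.2 h at p = 0.80.

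**3. The metrics can differ in sign with no missing records**

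Suppose that, within a 2*24 h window, awake time falls from 32 to 26 h and ON time without troublesome dyskinesia falls from 19.2 to 17.0 h (assumed values). The count goes from 19.2 × 2 = 38.4 to 17.0 × 2 = 34.0 records, a fall of 4.4. The share goes from 19.2/32 = 60.0% to 17.0/26 = 65.4%, a rise. The choice of metric is therefore not just a choice of unit.

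**4. The 8-hour rule**

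8 h × 2 = 16 records. If ASLEEP records count towards the 16:

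| Asleep (h) | Awake records left | One record moves the share by |
|---|---|---|
| 0 | 16 | 6.25 points |
| 4 | 8 | 12.5 points |
| 6 | 4 | 25 points |
| 7 | 2 | 50 points |
| 8 | 0 | share undefined |

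If the rule required 8 hours of non-missing awake records, the denominator would never fall below 16.

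**The case against.** The strongest reply is that 9.2.3 is the methods section, states its input explicitly, and agrees with Table 2 on the post-baseline window. A programmer working from those two places would produce a share, and only a stale footnote would remain. That is probably what was intended, though it is an inference. It does not remove the conflict, because the footnote is a live instruction about what input was used, and it would be printed.

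On the 8-hour rule, the sentence comes straight after the definition of the input as awake records, so recorded data can be read as meaning those records. This is fair: the text is ambiguous rather than plainly wrong. Reaching two denominator records takes the unfavourable reading and a diary made up almost entirely of sleep.

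The 8-awake-hour diary in the illustration is deliberately sparse. Its floor is borrowed from 9.2.3, since the footnote states no minimum, and no document says how common such diaries would be.

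Stronger inferences are tempting but not supported:

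- A reader might infer that a two-day baseline sum would be set against a four-day post-baseline sum. Neither section prescribes this. The footnote uses equal 2*24 h windows, and 9.2.3 divides by awake records.
- A reader might infer that the proposed minimum makes each patient's share precise. It only ensures that the 8 hours are awake hours. Whether 8 hours is enough is a separate question.
- A reader might infer that the table would be unreadable either way. Under 9.2.3 the analysis itself is well defined, and the fault lies in its labelling.

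**Conclusion.** The point holds as an inconsistency within the SAP. Section 9.2.3 and the Table ON 1 footnote disagree on the metric, the baseline window and the post-baseline window, and one of them must change. The textual conflict rests on no assumption.

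Its numerical size depends on which text is programmed. Under 9.2.3 the estimate is unaffected and the footnote is wrong. Under the footnote, incomplete diaries create apparent change where there is none: −14.4 h in the sparse example and −9.6 h for one lost day, both assuming 16 awake hours a day and a constant 60% share. These are illustrations, not expected biases.

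The 8-hour wording is an ambiguity that needs clarifying, not a demonstrated error. The omission from Table 2 is a gap in the record of changes: the window and the test are logged, but the share is not.

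This is a secondary endpoint in a study whose SAP calls its efficacy tests exploratory and its significant findings indicative (Sections 5.1 and 5.8). The correction is worth making before the table is programmed. The primary safety evaluation is not affected.

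**What to change.** 1. Replace the Table ON 1 footnote with the 9.2.3 definition: records of ON without dyskinesia plus ON with non-troublesome dyskinesia, as a share of non-missing awake records. Give the windows separately: all measurements before Visit 2 for baseline, and 4*24 h before each of Visits 6 and 7. A single 4*24 h statement for all visits would misstate baseline.
2. In 9.2.3, change the minimum to at least 8 hours of non-missing awake records in each visit window.
3. Add a row to Table 2 logging the move from ON time to a share of awake records, with the reason.

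No conversion of the share into hours per day is needed; it would require a length of waking day that the documents do not give.

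The cost is SAP wording, with no new data. A few sparse diary timepoints that would have passed the literal 8-hour rule may become missing.
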